1.0 Study Summary

Study Title	Decision Making Study (Grant title: Mechanisms Explaining the Link Between Weight Discrimination and Poor Cardiovascular Health)
Study Design	Randomized clinical trial
Primary Objective	
 Identify early-stage cognitive, affective, behavioral, and physiological mechanisms activated by experimentally manipulated weight discrimination. Identify psychological and demographic variables that moderate effects of weight discrimination.
Secondary Objective(s)	N/A
Research Intervention(s)/ Investigational Agent(s)	Experimental (weight discrimination) manipulation vs. Control manipulation
IND/IDE # (see section 5)	N/A
Study Population	Adults \geq aged 18 years recruited from the local community
Sample Size	320
Study Duration for individual participants	135-140 minutes total
Study Specific Abbreviations/ Definitions	BMI = body mass index

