17.0 Data Management and Confidentiality

Statistical Design, Power, and Analysis Plan

We designed this study to have very high power for the main effects of weight discrimination (Aim 1) and to ensure sufficient sensitivity for moderation effects of psychological (Aim 2) and demographic variables (Aim 3).

➤ **Aim 1: Identify early-stage cognitive, affective, behavioral, and physiological mechanisms activated by experimentally manipulated weight discrimination.** We hypothesize that, relative to participants in the control condition(s), participants in the weight discrimination (experimental) condition (vs. control) will display more impaired self-regulation, higher negative emotion, lower positive emotion, more social withdrawal and comfort eating, lower self-efficacy and intentions for engaging in weight control behavior, and increased cortisol secretion.

Aim 1 power and analysis. Nine outcomes are assessed for the study (Table 1), hence we adopt a conservative Bonferroni adjustment when evaluating the primary hypothesis and use significance level $\alpha = 0.005$ to maintain familywise Type I error rate of 0.05. We assumed conservative effect size estimates, which were among the smallest observed in our pilot data.⁴⁸ We plan to recruit 160 subjects per condition for the study, which yields 90% power ($\alpha = 0.005$) to detect the medium Cohen's $d = 0.50$ between the control and experimental conditions.

Aim 1 analyses will use unadjusted ANOVA followed by analysis of covariance and multiple regression methods that permit adjustment for age and other baseline characteristics that may exhibit imbalance across experimental conditions. To analyze effects of the manipulation on cortisol secretion (assessed at 3 timepoints), we will calculate the area under the curve (AUC) with respect to ground (AUCg).¹²⁰ For all Aims, residual diagnostics will assess model assumptions (e.g., normality, homogeneity) and responses will be transformed if necessary. Effect of experimental weight discrimination will be reported for both unadjusted and adjusted analyses.

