➤ **Aim 2: Identify psychological variables that moderate effects of weight discrimination.** We hypothesize that the effect of weight discrimination (vs. control) will be stronger for individuals who score higher on certain psychological variables (i.e., internalized weight bias, neuroticism) and weaker for individuals who score higher on other variables (i.e., self-compassion, conscientiousness; See Table 2). In other words, possessing some traits will be protective, while possessing other traits may render individuals more vulnerable to the harmful effects of weight discrimination.

Aim 2 power and analysis. The very high power of these designs for the primary hypotheses of Aim 1 ensures sufficient power for Aim 2 and additional analyses.

PROTOCOL TITLE: Decision Making Study

Statistical analysis will use multiple regression with condition assignment, the moderator, and their interaction as predictors and focus on interpretation of the coefficient for the interaction.¹²¹ With a continuous moderator, the coefficient for the interaction is the difference in the slope coefficients associated with the moderator in each of the treatment groups. Because these slopes are proportional to the correlation between the moderator and outcome in each group, respectively, the test of no moderation is equivalent to the test of equal correlation between moderator and outcome in all groups. Using Fisher's z transform of the correlations to approximate normality, The study (with 160 subjects in each of two conditions) provides 90% [80%] power (2-sided, $\alpha = 0.05$) to detect the change in correlation between moderator and outcome from 0.65 to 0.39 [0.43] associated with treatment assignment.¹²² Additional statistical analyses will adjust for baseline characteristics by including these as additional predictors in the model; estimated moderation effects will be reported for both unadjusted and adjusted analyses.

➤ **Aim 3: Identify demographic characteristics that moderate effects of weight discrimination.** We will conduct exploratory analyses to assess whether the negative effects of weight discrimination are moderated by age, sex/gender, race, and ethnicity.

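### Aim 2's 90% [80%] power belongs to a comparison of correlations, not to the planned interaction test, and the plan leaves Aim 2's confirmatory status and multiplicity control unstated

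*Combined protocol and SAP*

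**What the plan says.** All of this is in section 17.0 unless another section is named.

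- **Planned test.** "Statistical analysis will use multiple regression with condition assignment, the moderator, and their interaction as predictors", with interpretation resting on the interaction coefficient.
- **Power.** The plan argues that the slopes are proportional to the correlations, so that "the test of no moderation is equivalent to the test of equal correlation between moderator and outcome in all groups". With 160 per condition and two-sided 0.05 it then quotes 90% [80%] power, by Fisher's z, for a correlation of 0.65 in one condition against 0.39 [0.43] in the other. It also says: "The very high power of these designs for the primary hypotheses of Aim 1 ensures sufficient power for Aim 2 and additional analyses". The Aim 3 paragraph describes power for age as a moderator as similar.
- **Sample size.** The number per arm is tied to Aim 1: "We plan to recruit 160 subjects per condition for the study, which yields 90% power".
- **Multiplicity.** For Aim 1: "Nine outcomes are assessed for the study (Table 1), hence we adopt a conservative Bonferroni adjustment". No adjustment is stated for Aim 2; the only level given is two-sided 0.05.
- **Status.** The Primary Objective in section 1.0 includes "Identify psychological and demographic variables that moderate effects of weight discrimination". Sections 2.0 and 17.0 give directional hypotheses for internalized weight bias, neuroticism, self-compassion and conscientiousness. Aim 3 is called exploratory; Aim 2 is not. Section 17.0 uses the term primary hypothesis only for Aim 1.
- **Adjustment.** After the basic model, further models add baseline covariates, and "estimated moderation effects will be reported for both unadjusted and adjusted analyses".

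**The concern.** A slope equals the correlation multiplied by SD(outcome)/SD(moderator). Equal slopes and equal correlations are therefore the same hypothesis only if that SD ratio is the same in both arms. The plan gives no SDs and does not state this condition. Even where the two hypotheses coincide, the two tests use different standard errors and have different power. The quoted figure therefore cannot show what a null interaction would rule out.

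The second issue is interpretation. Section 3.0 says that moderator testing will identify vulnerable and resilient individuals and help to target interventions. A reader of the results needs to know whether an Aim 2 interaction is a confirmed finding, and at what error rate. The plan does not say.

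**Working it through.** **Inputs from section 17.0:** 160 per arm; two-sided 0.05 (critical value 1.960); correlations 0.65 against 0.39 [0.43]; nine outcomes; four psychological moderators. **Assumed, because the plan gives no SDs:** equal moderator SD in both arms, set to 1 (section 4.0 has the moderators measured before the lab session). Outcome SDs are taken two ways below.

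**1. The plan's own figure (Fisher z).** Power = Φ(q/SE − 1.960), with q = atanh(r1) − atanh(r2) and SE = √(2/157) = 0.1129.
- 0.65 against 0.39: q = 0.7753 − 0.4118 = 0.3635; power 89.6%.
- 0.65 against 0.43: q = 0.7753 − 0.4599 = 0.3154; power 79.8%.

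The stated 90% [80%] reproduces.

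**2. The planned test (difference of two regression slopes).** Power = Φ(|b1 − b2|/SE − 1.960), with SE = √((s1² + s2²)/160), where s1 and s2 are the residual SDs.
- *Equal total outcome SD (set to 1).* Slopes equal the correlations and s² = 1 − r². For 0.39: 0.26/√((0.5775 + 0.8479)/160) = 2.755; power 78.7%. For 0.43: 0.22/√((0.5775 + 0.8151)/160) = 2.358; power 65.5%.
- *Equal residual SD (set to 1).* b = r/√(1 − r²), so b1 = 0.8553 and b2 = 0.4235 [0.4763]; SE = √(2/160) = 0.1118. The ratios are 3.862 [3.390]; power 97.1% [92.4%].
- *Simulation check, 20,000 trials:* 78.0% [64.7%] and 96.7% [91.8%].
- *Limiting case.* If the outcome SD in the lower-correlation arm is 0.65/0.39 = 1.67 [0.65/0.43 = 1.51] times the other, the slopes are identical. There is then no moderation on the slope scale, although the correlations still differ.

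**3. Sensitivity of the planned test, equal residual SD.** Detectable slope difference = (z for alpha + z for power) × √(2/160), in residual SDs per moderator SD.
- At 0.05: (1.960 + 1.282) × 0.1118 = 0.36 for 90%; (1.960 + 0.842) × 0.1118 = 0.31 for 80%.
- At 0.05/36: (3.197 + 1.282) × 0.1118 = 0.50; (3.197 + 0.842) × 0.1118 = 0.45.

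**4. Multiplicity with no true moderation.** The plan does not write the number of tests. Crossing 4 moderators with 9 outcomes gives 36.
- *Independent tests:* either direction 1 − 0.95^36 = 84%; hypothesised direction only 1 − 0.975^36 = 60%.
- *Correlated tests:* assumed exchangeable correlations, variables scored toward harm or risk, 100,000 simulated runs.

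| Outcome r / moderator r | Either direction | Hypothesised direction |
|---|---|---|
| 0.2 / 0.3 | 80% | 49% |
| 0.2 / 0.5 | 76% | 45% |
| 0.5 / 0.3 | 69% | 39% |
| 0.5 / 0.5 | 64% | 34% |

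**The case against.** **On power.** The plan says that residual diagnostics will check homogeneity for all aims. Under equal residual SDs the planned test has 97% [92%] power, so the quoted figure is conservative. The lower 79% [65%] requires unequal residual variances. This stands. A reader might infer that Aim 2 is underpowered; the documents do not support that. Section 17.0 does say that the design was meant to give adequate sensitivity for moderation, but the 160 per arm is justified by Aim 1.

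**On status.** A reader might infer from the Primary Objective that Aim 2 is confirmatory and needs the same error control as Aim 1. The same bullet covers demographic moderators, which the plan explicitly calls exploratory, so being listed there settles nothing. Section 17.0 reserves the term primary hypothesis for Aim 1, and leaving non-primary interactions unadjusted is common practice. What remains is that Aim 2 is neither called exploratory nor given a rule, while its hypotheses are specific and directional.

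**On the false-positive risk.** A reader might infer that a false moderator claim is more likely than not. Since Aim 2 fixes a direction for all four moderators, a result the other way would not support it. In the hypothesised direction the chance is below one half in every correlated case examined. A reader might also count the adjusted estimates as a second set of chances. The plan introduces them as additional to the basic model and nowhere says that either version may decide.

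**Conclusion.** The concern holds in two limited parts.

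First, the claim of equivalence is wrong, and 90% [80%] is not the power of the planned test. The correct figure depends on SDs that the plan does not give. The stated power is too low under the homogeneity assumption that the plan intends to check and too high if total outcome SDs are equal. This is a misdescribed sensitivity statement, not evidence that the sample is too small.

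Second, Aim 2's status is unclear and no multiplicity control is stated. The 60% and 34-49% figures rest on the derived count of 36 tests, no true moderation, two-sided 0.05 for each test, and, for the lower range, the assumed correlations. They show why the status must be stated; they do not predict the trial's results.

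The statement that Aim 1 power ensures Aim 2 power is a minor further fault: power for a main effect does not carry over to an interaction.

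**What to change.** 1. **Power text.** Delete the equivalence statement and the sentence that derives Aim 2 power from Aim 1. State instead that, with 160 per arm, two-sided 0.05 and equal residual SD, a single interaction test on a continuous outcome has 90% [80%] power for a slope difference of 0.36 [0.31] residual SD per moderator SD. Point the age sentence under Aim 3 to this figure. Say that it does not apply to social withdrawal if that is analysed as a choice among options. The documents differ on this: section 4.0 and one part of section 6.0 describe the extent of a preference, while the script in section 6.0 asks for one of three options.
2. **Status and multiplicity.** Either label Aim 2 exploratory, like Aim 3, or apply one stated rule, for example Benjamini-Hochberg at 5%, to the unadjusted interaction tests, with the adjusted models as sensitivity analyses. If a rule is applied, add that at its strictest step for 36 tests (0.05/36) the detectable difference rises to 0.50 [0.45]. Benjamini-Hochberg controls the false discovery rate, not the familywise rate used for Aim 1, and the text should say so.

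**Cost.** SAP wording only; design, sample size and data collection are unchanged. If a rule is adopted, stated sensitivity is less favourable and fewer moderators may be declared.

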Identifying moderating variables will guide interventions to reduce the harmful effects of weight discrimination. Previous research has largely failed to examine variables that moderate effects of weight discrimination on poor health outcomes. To address this gap, we will identify both psychological variables (Aim 2) and demographic characteristics (Aim 3) that moderate responses to experimentally manipulated weight discrimination. Our pilot work identified several promising psychological moderators. For example, one candidate is internalized weight bias, or the extent to which people devalue and stigmatize themselves for their weight. In our pilot work, participants with higher internalized weight bias were more likely to view a negative social interaction as reflecting weight discrimination and, in turn, to display more negative affect, poorer self-esteem, and higher self-regulation failure. Replicating this finding in the current project would identify a valuable intervention target for mitigating the harmful effects of weight discrimination. Identifying demographic moderators (e.g., race, ethnicity, sex/gender) will also be useful for personalizing interventions to those groups with the highest need.

Using a rigorous experimental approach, we will identify moderators of and mechanisms through which weight discrimination undermines cardiovascular health. Identifying moderators and mechanisms is a critical first step for intervention development.³⁶ By intervening on early-stage mechanisms, we can prevent the cascade of downstream processes that contribute to poor cardiovascular health.

INNOVATION

We will use an experimental approach to manipulate weight discrimination.

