Psychological moderators. Further, participants high in internalized weight bias (IWB) and neuroticism were more likely to view the negative feedback as reflecting weight discrimination and to report more negative emotions, whereas participants high in self-compassion and conscientiousness demonstrated the opposite pattern. Findings support Aim 1 by demonstrating effects of weight discrimination on negative emotions and self-regulation and Aim 2 by identifying psychological moderators.

Pilot Study 3: Cognitive, Affective, and Behavioral Correlates of Expectations of Rejection. This lab study identified individual differences associated with expectations of rejection during a novel social interaction and the implications of those expectations for psychological and behavioral outcomes. Before completing a task with a partner (a member of the study team), adults with obesity (N=111) reported the extent to which they thought they would be accepted vs. rejected by their partner. Participants who anticipated rejection by their partner reported more distress and anxiety. Expectations of rejection were also associated with social withdrawal, indicated by participants choosing to work by themselves to avoid further social interaction.

Psychological moderators. Participants high in internalized weight bias and neuroticism reported higher expectations of rejection, more distress and anxiety, and greater social withdrawal. In contrast, participants high in self-compassion demonstrated the opposite pattern. These findings demonstrate support for Aim 2.

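### Adjusting the Aim 2 moderation models with main-effect covariates does not separate correlated traits, so a trait named as an intervention target may only be a proxy for another

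*Combined protocol and SAP*

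**What the plan says.** Section 17.0, under Aim 2 power and analysis, gives the model: "Statistical analysis will use multiple regression with condition assignment, the moderator, and their interaction as predictors". Adjustment follows: "Additional statistical analyses will adjust for baseline characteristics by including these as additional predictors in the model", and "estimated moderation effects will be reported for both unadjusted and adjusted analyses". No covariate-by-condition product appears under Aim 2 or Aim 3, nor does a model containing more than one moderator's interaction. The only stated reason for choosing covariates is under Aim 1, where the methods are to permit "adjustment for age and other baseline characteristics that may exhibit imbalance across experimental conditions".

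Table 2 in Section 3.0 lists four psychological candidates: internalized weight bias and neuroticism as risk factors, self-compassion and conscientiousness as resilience factors. All are measured in the online survey before the lab session (Section 4.0).

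Section 3.0 puts a moderator finding to two uses. One is as something to intervene on; of the pilot result for internalized weight bias it says "Replicating this finding in the current project would identify a valuable intervention target". The closing summary of that section again speaks of modifiable targets. The other, in the same summary, is to identify people who are more vulnerable or more resilient.

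**The concern.** Condition is randomised; the traits are not. Randomisation protects the effect of condition at any level of a trait, but it does not show that this trait, and not another correlated with it, is responsible for the difference in effect.

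The four traits could plausibly be correlated. In Pilot Study 2, "participants high in internalized weight bias (IWB) and neuroticism were more likely to view the negative feedback as reflecting weight discrimination", and self-compassion and conscientiousness showed the opposite pattern. That is suggestive only: the protocol reports how each trait related to attribution and emotion, not how the traits related to each other.

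Suppose one trait is the true moderator and a second is merely correlated with it. Testing the second leaves the first trait's product with condition out of the model, and the tested product absorbs it. Adding the first trait as a main effect does not help, because the omitted term is the product. A reader who sees adjusted and unadjusted moderation effects agree may take that as evidence that confounding has been dealt with. What is at stake is the choice of trait for later intervention work.

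**Working it through.** **Inputs from Section 17.0.** 160 per arm; two-sided 0.05; moderator-outcome correlation 0.65 in one arm and 0.39 [0.43] in the other; stated power 90% [80%].

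**Assumed.** The correlation ρ between two traits, shown over a range.

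**Step 1: the plan's figure.** Fisher's z with n = 160 per arm: power = Φ(|atanh(r1) − atanh(r2)| / √(2/(n − 3)) − 1.96).
- 0.65 vs 0.39: (0.7753 − 0.4118) / √(2/157) = 0.3635 / 0.1129 = 3.22; Φ(3.22 − 1.96) = 89.6%.
- 0.65 vs 0.43: (0.7753 − 0.4599) / 0.1129 = 2.79; Φ(2.79 − 1.96) = 79.8%.

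Both stated figures reproduce. They apply to one moderator considered alone.

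**Step 2: why a main effect does not help.** Let M be the true moderator, P a proxy with correlation ρ to M and no moderating effect of its own, both standardised, and c the centred condition indicator. The effect left out is g·c·M. By randomisation, c·M is uncorrelated with c, P and M. Its projection on c·P is cov(cM, cP)/var(cP) = ρ. The expected coefficient of c·P is therefore g·ρ, whether or not M is in the model as a predictor. With outcome SD 1 in each arm, g = 0.65 − 0.39 = 0.26, giving 0.078, 0.130 and 0.156 at ρ = 0.3, 0.5 and 0.6. Adding c·M makes it zero.

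**Step 3: how often the proxy is declared a moderator.** Simulation at 0.65 vs 0.39, N = 320, at least 6,000 trials per setting:

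| ρ | P only | M added as predictor | M and M × condition added |
|---|---|---|---|
| 0 | 5% | 5% | 5% |
| 0.3 | 11% | 13% | 5% |
| 0.5 | 22% | 27% | 5% |
| 0.6 | 32% | 37% | 5% |
| 0.7 | 41% | 47% | 5% |

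At ρ = 0.5 the mean P × condition coefficient was 0.132, 0.130 and −0.001 across the three models, as Step 2 predicts. The middle column slightly exceeds the first because adding M lowers the residual variance while the bias stays.

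**Step 4: other effect sizes.** With residual SD 1 and M added as a predictor, true moderation of 0.35 SD per SD gives about 15%, 33% and 45% at ρ = 0.3, 0.5 and 0.6; true moderation of 0.20 gives about 9%, 14% and 19%.

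**Step 5: the price of separating the traits.** Take four equally correlated traits of which one moderates, at 0.65 vs 0.39. Fitted alone, its regression interaction has about 78% power. This is below the 90% of Step 1 because the regression test uses the slope difference: SE ≈ √[(1 − 0.65² + 1 − 0.39²)/160] = 0.094, 0.26/0.094 = 2.75, Φ(2.75 − 1.96) ≈ 79%.

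With all four traits and four products in the model, the variance inflation is (1 + 2ρ)/[(1 − ρ)(1 + 3ρ)], whose square root is 1.10, 1.26 and 1.40 at ρ = 0.3, 0.5 and 0.6. Simulation gives SE increases of about 11%, 28% and 42%, and power of about 68–71%, 57% and 49%.

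**The case against.** The strongest reply is that the plan may not be asking the causal question. The Aim 2 hypotheses concern people who score higher or lower on each trait, and one stated use is to identify vulnerable individuals. For that purpose the single-trait interaction is the right quantity: a correlated trait's interaction is real effect modification, and the rates above are not false positives. This stands, and it is why the single-moderator tests should stay. It does not cover the other stated use, as an intervention target.

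Three further objections hold in part:
- **Purpose of adjustment.** The plan never says adjustment is meant to separate traits, nor that the other psychological traits will be covariates. A reader might infer that it claims to deconfound moderation; the text does not support that. Nor does it rule out product terms or a joint model. The point is that neither is specified.
- **Size of the harm.** A reader might infer that several correlated traits will all appear to moderate and that adjustment will confirm each of them. The figures do not support this: even at ρ = 0.6 the pure proxy is missed in about 63% of trials. The scenario also gives the proxy no effect of its own, whereas the protocol expects all four traits to moderate.
- **Trait correlations.** A reader might infer from the pilots that the traits are strongly correlated. No correlation between traits is reported, and Pilot Study 3 does not mention conscientiousness.

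**Conclusion.** The concern holds for trait-specific and intervention-target conclusions, not for descriptive ones. Adjustment by additional predictors, as written, removes none of the confounding of an interaction. At the plan's own effect size, a pure proxy would be declared a moderator in about 13%, 27% and 37% of trials at trait correlations of 0.3, 0.5 and 0.6, against 5% when the competing product is included.

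These rates assume that one trait is the sole moderator, that the proxy has no effect of its own, and that the true moderator happens to be among the covariates. The correlations are assumed, and at zero there is no problem. It would be wrong to infer that the Aim 2 tests are invalid or that the stated Fisher-z power is miscalculated: the first remain sound for describing who reacts more strongly, and the second reproduces. The Aim 1 comparisons are untouched. This is a worthwhile, low-cost improvement to how Aim 2 is analysed and worded.

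**What to change.** Amend the Aim 2 analysis text in Section 17.0 as follows:

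1. Keep the single-moderator models as the main Aim 2 tests, and describe their results as markers of vulnerability or resilience.
2. For each outcome, add one supporting joint model with condition, the four centred psychological traits and their four products with condition, reported as estimates with confidence intervals.
3. Where a covariate is included to address confounding of a moderator, include its product with condition as well. This need not apply to every baseline characteristic.
4. Use trait-specific or intervention-target wording only with the joint-model estimate shown alongside. Do not read non-significance in that model as absence of moderation.

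For Aim 3, which is labelled exploratory, the same form is optional.

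The cost is a few sentences and one extra model per outcome, with no new data. The joint model is less precise by the amounts in Step 5; at a correlation of 0.6 it would miss a true moderator about half the time. It should therefore inform interpretation and not serve as a pass-or-fail rule.
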